For participants who have a case of ARVI (COVID-19), visit 3 can be carried out earlier or later, but the total duration of the study should not be more than 90 days. Up to this point, medical researcher should try to collect the most complete information about the patient's condition. If it is not possible to conduct a face-to-face visit, final visit is conducted remotely.

Schedule of research procedures

| Visit number | 0 | 1 | 2 | 3 |
|---|-----------|---------------|--|--|
| Setting | In person | In person | Phone call | In person |
| Visit name | Screening | Randomization | The end of the course of prevention Beginning of the observation period | End of the observation period Completion of the study |
| Study days | -3-1(0) | 0 | 27 (+/-3) | 56-62* |
| Informed consent ¹ | + | | | |
| Anamnesis ² | + | | | |
| Complaints | + | + | + | + |
| Physical examination ³ | + | + | | + |
| Pregnancy test | + | | | |
| Safety assessment | + | + | + | + |
| Analysis for RNA to SARS-CoV-2 ⁴ | + | | | + |
| Checking the inclusion/non-inclusion criteria | + | + | | |
| Checking exclusion criteria | | | + | |

⁷ A full-time visit can be carried out both at the research center and at home

| | | | | |
|--|---|---|---|----------------|
| Randomization | | + | | |
| Delivery of the study drug ⁵ | | + | | + |
| Compliance assessment | | | + | + |
| Issue of the participant's diary | | + | | |
| Effectiveness evaluation | | | + | + |
| Assessment of the participant's condition according to the WHO scale | + | + | + | + ⁷ |
| Return of study drug and diary | | | | + |

* For patients with a registered case of ARVI, duration of participation in the study may be longer, but not exceed 90 days

- 1 All research procedures, except routine laboratory and instrumental studies, the data of which are used to assess the condition of the study participant, are performed after the procedure of signing the informed consent of the patient
- 2 The study should indicate the epidemiological history of respiratory viral diseases, status of vaccination (influenza, pneumonia, COVID-19), use of means of nonspecific protection and prevention of acute respiratory viral infections, including COVID-19

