- 3 It includes a standard examination by a doctor, including: thermometry, assessment of visible mucous membranes of the upper respiratory tract, auscultation and percussion of the lungs, palpation of lymph nodes, examination of abdominal organs with determination of the size of the liver and spleen, assessment of the level of consciousness; clinical history; measurement of height, weight, respiratory rate, heart rate, blood pressure, pulse oximetry with measurement SpO₂
- 4 Within the framework of this study, results of tests performed no later than 72 hours before screening can be accepted at the screening visit; if the PCR test is received as "controversial", patient excluded of the study according to non-inclusion criterion No. 5 and cannot be re-screened further.
- 5 At the randomization visit, drug is given to participants assigned to the study group immediately for 2 courses (2 vials) with instructions for use and preparation. Upon completion of the study, participants of the control group can also optionally receive 1 vial of the study drug as a means of preventing acute respiratory viral infections for use as part of the instructions for medical use.
- 6 If performed as part of a routine practice
- 7 In case of registration of ARVI at the final visit 3, in parallel with the current assessment of the participant's condition, an additional assessment of the case is carried out according to the WHO scale, reflecting the maximum clinical manifestation of the disease.

Rules for stopping research

The sponsor has the right to stop the research at any time. Also, the study may be stopped prematurely by the decision of the IEC or regulatory authorities.

In case of early closure of the research center, all research documentation (except for the one that should remain in storage at the center) must be returned to the sponsor. Research documents, including primary medical records, must be kept at the center for at least 15 years after the completion of the study.

METHODOLOGY OF NON-INTERVENTIONAL RESEARCH

Randomization of study participants

During randomization, patients are randomly distributed in a 1:1 ratio into two groups: Group I (main) and Group II (control).

According to the methodology approved by this protocol, the participant must use (Group I) or not use (Group II) study drug (depending on the distributed randomization number at Visit 1) for 27 days of the preventive course (10 days + 7 days + 10 days).

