In case of a positive PCR test before the start of the drug, volunteer is not included in the study, is isolated and falls under the supervision of a district doctor. In case of a positive PCR test during or after the preventive course, volunteer continues to participate in the study, is isolated under observation and, if possible, comes to visit 3 after the quarantine is lifted (at least 14 days from the date of signing Consent for the treatment of a new coronavirus infection COVID-19 in outpatient conditions (at home) and observing the isolation regime or discharge from the hospital in case of laboratory confirmation of COVID-19) with the provision of data on their condition to the researcher coordinator.

STUDY POPULATION

Adult volunteers who do not have clinical symptoms of ARVI.

Inclusion criteria

1. Volunteers of both genders over 18 years old.
2. Obtaining a written form of informed consent.
3. Ability and consent to participate in this study.
4. No symptoms of respiratory infection.
5. A negative result of a PCR study for the presence of SARS-CoV-2 RNA according to the biomaterial obtained by nasopharyngeal ⁹smear.

Non-inclusion criteria

1. Any other concomitant diseases or conditions that, in the opinion of the research doctor, may distort the results of the study, restrict the rights of the volunteer, or put him at greater risk.
2. Contraindications to the use of the study drug.
3. Individual intolerance of the ingredients included in the composition of the study drug.
4. Pregnancy or breast-feeding.
5. Controversial result of PCR test for the presence of SARS-CoV-2 RNA according to the biomaterial obtained by nasopharyngeal smear.
6. Participation in a clinical trial using the investigated therapy for 30 days prior to inclusion in this study.
7. Disagreement on following reliable contraceptive measures in the framework of the study

⁹ It is permissible to accept the results of a nasal or pharyngeal smear, as well as the results of studies performed before inclusion in the study for no more than 72 hours.

(sexual abstinence; or a combination of 2 different methods: for example, barrier and spermicides, or barrier and intrauterine device, or barrier and hormonal, etc.) – for participants with preserved childbearing potential.

Number of participants

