In this study, the main parameter of effectiveness is the proportion of patients with acute respiratory viral infections, including COVID-19, at the end of the period of preventive administration of the drug. The study is planned to show that in the study group, the number of patients with acute respiratory viral infections, including COVID-19, will be significantly less compared to the control group.

The efficiency parameter was selected based on international recommendations for manufacturers of medicines and biological products [28].

The null hypothesis will be tested by comparing the number of cases in the two groups at the end of the period of preventive administration of the drug. It is expected that at least 90% of randomized patients will be suitable for inclusion in the population of the primary analysis (PP). The statistical purpose of the study is a comparative study of the effectiveness of the preventive regimen of the drug. In the main group of study I, study drug Ingaron 100,000 IU, lyophilizate, will be used to prepare a solution for intranasal administration, 1 time a day every other day for 10 days with a repeat of the 10-day course of preventive administration after 7 days of interruption.

To estimate the sample size in this study, an 80% power level was taken (P – probability of not missing the present effect is 0.8) and a one-sided level of statistical significance of 5% (α – the probability of making an erroneous decision about the presence of an effect is less than 0.05). The statistical criteria used are one-sided due to the availability of information about the superiority of the effect of the study drug over the lack of preventive measures against the nosology being studied [28].

Thus, the sample size was calculated based on the following parameters:

- at the required significance level $\alpha = 0.05$, the value of $Z = 1.96$;
- level of statistical power is assumed to be 80%, the value of $Z = 0.84$;
- method of sample formation – randomization using random elements.

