Address of the place of manufacture: [name], J.S.C. "Biomed"-Mechnikov Tel/[contact], [name]

E-mail: [contact] Internet: www.pharmaclon.ru

Labelling: The inscription "For post-marketing research RAIN-2020" is applied to the primary packaging and secondary (consumer) packaging of the study drug product, the inscription "Not for sale" is additionally applied to the secondary (consumer) packaging in accordance with the requirements of the Federal Law "On Circulation of Medicines" dated 12.04.2010 N 61-FZ as amended Federal Law No. 429-FZ from 22.12.2014.

Compliance assessment

Assessment of compliance with study preventive therapy is evaluated on the basis of data recorded in the participant's diary, on visit 3, as well as in advance as part of an oral survey of the participant on a phone call visit after the end of preventive use of the drug. Compliance is assessed on a 100% scale, where:

100% – participant completed 2 cycles of 10-day courses without violating the dosage regimen and the frequency of admission

90% – participant completed 2 cycles of 10-day courses with a single violation of dosage regimen or dosage frequency

80% – participant completed 1 cycle of the 10-day course without violating dosage regimen or dosage frequency

70% – participant completed 2 cycles of 10-day courses with a double violation of dosage regimen or dosage frequency (single violation of each course)

60% – participant completed 1 cycle of 10-day course with a single violation of dosage regimen or dosage frequency

50% or less – participant completed 1 or 2 cycles of 10-day courses with a systematic (twofold or more) violation of the dosage regimen or dosage frequency in each of the courses (non-compliance with a single dose, frequency of use and/or its duration).

Compliance of 50% or less is the criterion for excluding a participant from the study.

STUDY PARAMETERS OF EFFICIENCY AND SAFETY

Effectiveness criteria

Effectiveness criteria will be evaluated according to the data recorded in the participants' diaries, in primary medical documentation.

Primary effectiveness criterion:

The proportion of patients with acute respiratory viral infections, including COVID-19, at the end of the period of preventive administration of the drug (measurement time: 28 days).

Secondary effectiveness criterion:

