1. The proportion of patients with confirmed COVID-19 at the end of the period of preventive treatment of the drug (measurement period: 28 days).
2. The proportion of patients with acute respiratory viral infections, including COVID-19, at the end of the follow-up period (change period: 2 months).
3. The proportion of patients with confirmed COVID-19 at the end of the follow-up period (change period: 2 months).
4. Frequency of development of complicated course of ARVI.
5. The proportion of participants with each of the scores (0-8) according to the WHO Clinical Improvement Scale (change period: 28 days).
6. The proportion of participants with each of the scores (0-8) according to the WHO Clinical Improvement Scale (change period: 2 months).
7. Duration of symptoms of the disease of study participants who had acute respiratory viral infections, including COVID-19 (change period: 2 months).
8. The duration of the symptoms of the disease of the study participants who were infected with ARVI, including COVID-19 (measurement period: 28 days).

Confirmation of clinical cases of ARVI, including COVID-19:

In the following cases:

- 1) a positive result of PCR on SARS-CoV-2 RNA, regardless of the presence of clinical symptoms;
- 2) appearance of clinical symptoms of ARVI in the absence of a PCR result on SARS-CoV-2 RNA or in the case of a negative result on SARS-CoV-2 RNA, -

at any stage during participation in the study, a completion visit (Visit 3) is conducted at the end of the quarantine period (at least 14 days from the date of signing Consent for the treatment of a new COVID-19 coronavirus infection in outpatient settings (at home) and compliance with the isolation regime or discharge from the hospital in case of laboratory confirmation of COVID-19), at which the patient returns the participant's diary and reports his condition to the doctor-researcher, transmits information about hospitalization, duration of symptoms, results of tests and performed studies.

Definition of the COVID-19 case:

Suspicious case of COVID-19

Body temperature above 37.5° in addition to one or more of the following signs (in the absence of other known causes that explain the clinical picture, regardless of the epidemiological history):

- Cough (dry or with scant sputum)
- Shortness of breath
- Feeling of congestion in the chest
- SpO₂ no more than 95%
- Sore throat
- Nasal stuffiness or moderate rhinorrhea
- Smell disorders or anosmia
- Ageusia
- Conjunctivitis
- Fatigue

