5.5. Populations of participants for analysis

The following populations will be formed for analysis: ITT, PP and safety; additionally: ITT_NV, PP_NV, ITT_NV_BE, PP_NV_BE.

Statistical data analysis will be carried out in the following populations of participants:

1. Population of all included and randomized participants (intention-to-treat, ITT): all randomized participants who were exposed to the study drug, regardless of the degree of protocol compliance during the study. This data set is the main one for the analysis of primary and secondary effectiveness parameters;
2. Population of participants who completed the study according to the protocol (per protocol, PP): all randomized subjects who completed participation in the study in accordance with the protocol (completed the prescribed period of treatment and follow-up without significant deviations from the protocol). This data set is additional for the analysis of primary and secondary effectiveness parameters;
3. Safety population: The data set analyzed for safety assessment is identical to the ITT data set. However, unlike the population depending on the prescribed treatment, participants are analyzed depending on the actual treatment (if it differs from the treatment that was prescribed by randomization). All types of safety analysis will be based on the use of a data set for security assessment;
4. Modified population of all included and randomized participants (intention-to-treat, ITT) not vaccinated against COVID-19: ITT_NV. This data set is additional for the analysis of the primary efficiency parameter;
5. Modified population of participants who completed the study according to the protocol (per protocol, PP), not vaccinated against COVID-19: PP_NV. This data set is additional for the analysis of the primary efficiency parameter;
6. Modified population of all included and randomized participants (intention-to-treat, ITT) not vaccinated against COVID-19 or vaccinated before inclusion in the study: ITT_NV_BE. This data set is additional for the analysis of the primary efficiency parameter;
7. Modified population of participants who completed the study according to the protocol (per protocol, PP), not vaccinated against COVID-19 or vaccinated before inclusion in the study: PP_NV_BE. This data set is additional for the analysis of the primary efficiency parameter.

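### The per-protocol definition has no cut-off at ARVI onset, so Group I cases can drop out of PP for what happens after they fall ill, which would favour the drug

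*SAP*

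**What the plan says.** SAP 5.5 item 2 defines PP as randomised participants who "completed the prescribed period of treatment and follow-up without significant deviations from the protocol". Of its role it says: "This data set is additional for the analysis of primary and secondary effectiveness parameters". PP_NV and PP_NV_BE are vaccination-status subsets of the same set. SAP 5.1 makes ITT the main analysis of the primary endpoint and PP the additional one. The closing text of SAP 5.5 restates PP in terms of *critical* rather than *significant* deviations. Neither term is defined.

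The Protocol rules that feed this definition are:

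- **Course length** (Randomization of study participants): 10 + 7 + 10 = 27 days.
- **Compliance** (Compliance assessment): a scale written in terms of drug cycles, with the rule "Compliance of 50% or less is the criterion for excluding a participant from the study". One clean cycle scores 80%.
- **Prohibited therapy**: Group I may not use any medicine with a possible ARVI-preventive effect. Group II is barred only from interferon gamma. Breach is exclusion criterion 1. No time limit at illness onset is given.
- **Handling of cases**: after a positive PCR the "volunteer continues to participate in the study, is isolated under observation and, if possible, comes to visit 3 after the quarantine is lifted". For a case of ARVI, "a completion visit (Visit 3) is conducted at the end of the quarantine period", and the design section adds that "visit 3 can be carried out earlier or later, but the total duration of the study should not be more than 90 days".

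**The concern.** PP membership is decided partly by what a participant does after the primary endpoint has been reached. Once someone has had ARVI, later missed drops or later medication say nothing about whether the drug was taken as intended while it could still have prevented that illness. Under the present wording they can still remove the case from the numerator.

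The rules that can do this weigh on one arm. Only Group I has drops to miss, and only Group I faces the broad medication ban. Any selective loss would therefore mainly take cases out of Group I and lower its PP rate. The trial is open-label and disqualifying deviations are undefined, so classification would rest on judgement made with knowledge of arm and outcome.

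PP is there to test the sensitivity of the ITT result, and PP, PP_NV and PP_NV_BE are three of the six populations listed for SAP Table 8. If they lean toward the drug, agreement with ITT would reassure more than it should.

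**Working it through.** **1. Group size.** The Protocol formula is n = (P1·Q1 + P2·Q2)·t² / (P1 − P2)². With P1 = 0.05, P2 = 0.02 and t = 1.96, this gives (0.0475 + 0.0196) × 3.8416 / 0.0009 = 286.4, against the stated 286. Multiplying by 1.10 gives 315.05, against the stated 315. I use 315 per arm. (The formula has no power term, which is a separate matter.)

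**2. How a case could leave PP, read from the text.**

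| Event after ARVI onset | Bears on | Effect on PP |
|---|---|---|
| Stops drops during cycle 1 | Group I only | No category fits; two or more missed doses sits closest to 50% or less, the exclusion threshold |
| Stops after one clean cycle | Group I only | Scores 80%, so not excluded from the study; on a strict reading of SAP 5.5, treatment was still not completed |
| Takes a medicine with possible ARVI-preventive effect | Group I only | Exclusion criterion 1, with no cut-off at onset |
| Visit 3 held early or late | Both arms | Expressly permitted, so not a deviation |

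**3. Rough ceiling for the compliance route.** The diary sets cycle 1 doses on Days 1, 3, 5, 7 and 9. Missing two of them through illness means onset by about Day 7. If onset were uniform over 28 days (an assumption), 7/28 = 25% of Group I cases fall there, and all would have to stop their drops for the full 25% to be lost. The other Group I routes could add to this by an amount the documents do not allow one to estimate.

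**4. Expected PP rates.** Let f be the share of an arm's cases lost from PP, with N = 315 and true incidence p = 0.05 in both arms, so Np = 15.75 cases. The PP rate is Np(1 − f) / (N − Np·f).

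- f = 0.10: 14.175 / 313.425 = 4.52%
- f = 0.15: 13.3875 / 312.6375 = 4.28%
- f = 0.25: 11.8125 / 311.0625 = 3.80%

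**5. Rate of p<0.05 in favour of the drug.** Simulation under no true effect: cases are binomial in each arm, the stated share is removed at random, and the SAP 5.1 test rule is applied (Fisher, Yates or Pearson by expected count, two-sided 0.05). A trial counts only if the Group I rate is the lower one. Ranges cover separate runs of 4,000 to 40,000 trials.

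| Group I cases lost | Group II cases lost | Expected PP rates, I v II | p<0.05 favouring drug |
|---|---|---|---|
| 0% | 0% | 5.00% v 5.00% | 2.2–2.7% |
| 10% | 0% | 4.52% v 5.00% | 4.6–4.8% |
| 25% | 0% | 3.80% v 5.00% | 11–12% |
| 25% | 15% | 3.80% v 4.28% | 4.4–4.6% |
| 25% | 25% | 3.80% v 3.80% | 2.3–2.4% |

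The inflation comes from the difference in loss between arms, not from loss as such.

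**The case against.** A reader might infer that ARVI cases are removed from PP because they fell ill, and that PP favours the drug by construction. The documents do not support that. ARVI is not among the ten exclusion criteria, no section stops the drops at ARVI, and PCR-positive participants stay in the study. *Significant* could reasonably be read as not covering doses missed through illness.

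A reader might also infer that an early Visit 3 costs a case its PP place. That does not hold either: the Protocol allows the visit to move for cases in both arms and calls it a completion visit.

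The compliance scale is also more forgiving than it first looks. One clean cycle scores 80% and one cycle with a single violation scores 60%. Illness in the break or in cycle 2 after a clean first cycle does not reach the 50% threshold.

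The calculation is conditional as well: its largest figures assume that no Group II case is lost. Losing half of Group I's cases would give about 33%, but a share that size exceeds the 25% ceiling of the compliance route and has no support in the text.

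All of this stands, and it limits the point to a possible loss of unknown size. It does not remove the gap. Staying in the study governs follow-up, not PP membership. A score of 80% avoids exclusion from the study, but it is not completion of the prescribed treatment as SAP 5.5 words it. Nothing protects a Group I case with onset in cycle 1, or one who takes a barred medicine after onset.

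**Conclusion.** The gap is real and worth closing before analysis. SAP 5.5 lets PP, PP_NV and PP_NV_BE depend on behaviour after the endpoint, and the rules that could cause loss bear on Group I, so any bias would favour the drug.

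The size cannot be derived from the documents. At 5% incidence with 315 per arm, no true effect and no Group II loss, an assumed 10% loss of Group I cases roughly doubles the chance of a result favouring the drug (about 5% against 2.5%). A 25% loss raises it to about 11%, with an apparent reduction of 5.00 − 3.80 = 1.20 percentage points, against the 3 points the trial was planned to detect.

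The harm is confined to the PP-based sensitivity analyses. ITT in the SAP, and the full analysis set in the Protocol's statistical section, remain the main population and are unaffected. The Protocol's sample-size section does call PP the population of the primary analysis. That label should be reconciled with the rest, but the present point does not depend on it.

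**What to change.** Change the analysis-set definition in SAP 5.5 only, for PP, PP_NV and PP_NV_BE:

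1. Judge adherence, prohibited therapy and completion up to the earlier of first ARVI onset and Day 28, counting only doses due before onset. For a PCR-positive case without symptoms, use the date of the positive test.
2. Keep a participant who was adherent until onset in PP as a case, whatever happens afterwards, including later exclusion from the study.
3. Count a Visit 3 brought forward because of ARVI as completion.
4. Report PP exclusions by arm and by case status, so that any remaining imbalance is visible.

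Use one term for disqualifying deviations throughout SAP 5.5 and define it before analysis. PP comparisons of the two-month endpoints need the same cut, with the end of follow-up in place of Day 28.

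The Protocol's compliance scale, prohibited-therapy rule and criteria for excluding participants from the study stay as they are. The cost is a few sentences in the SAP and one extra table. No new data are needed: cases are captured on the ARVI registration form named in SAP 5.1, and the diaries have fields for symptom start dates and, in Group I, dosing dates and times.
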